11. SAFETY EVALUATION

Safety evaluations will be conducted in accordance with GCP standards and applicable regulations. The sponsor has delegated management of adverse events (AEs) recorded during the study to the Spanish Clinical Research Network (SCReN), responsible for notifying regulatory authorities (AEMPS, regional health authorities) and CEIm of serious and unexpected adverse reactions (SUSARs), annual reports, or other relevant safety information.

I) Specification of Safety Parameters

Adverse Event (AE)

Any harmful incidence affecting the health of a patient or clinical trial subject treated with a medication, whether or not it has a causal relationship with the medication.

Adverse Reaction (AR)

Any harmful and unintended response to a medication. It refers to any harmful and unintended response to a medication, regardless of the dose administered.

Serious Adverse Reaction (SAR) / Serious Adverse Event (SAE)

Adverse events or reactions are considered serious if, at any dose, they result in death, pose a threat to the life of the subject, require hospitalization or prolong an existing hospitalization, cause permanent or significant disability or incapacity, or lead to a congenital anomaly or malformation. For reporting purposes, any suspected AE or AR deemed medically important will also be treated as serious, even if they do not meet the previous criteria, such as those that threaten the patient or require intervention to prevent any of the aforementioned outcomes, and any suspected transmission of an infectious agent through a medication.

Levels of Intensity

- **Mild** - Transient, without activity limitation, no medical intervention/treatment required.
- **Moderate** - Some activity limitation, some assistance may be needed, requires minimal or no medical intervention/treatment.
- **Severe** - Marked activity limitation, usually requires some form of assistance, requires medical intervention/treatment, hospitalization may be necessary.

Causality Criteria

The sponsor will classify adverse events based on their causal relationship with the drug according to the Karch and Lasagna (1977) algorithm as:

- **Definitive:** There is a reasonable temporal sequence between the administration of the drug and the occurrence of the AE. This event matches the ARs described

for the drug, improves with discontinuation of the drug, reappears upon re-administration, and cannot be explained by alternative causes.

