- **Probable:** There is a reasonable temporal sequence between the administration of the drug and the occurrence of the AE. This event matches the ARs described for the drug, improves after treatment is interrupted, and cannot be explained by other alternatives.
- **Possible:** There is a reasonable temporal sequence between the administration of the drug and the occurrence of the AE. This event matches the ARs described for the drug but may be explained by alternative causes.
- **Conditional or Unlikely:** There is a reasonable temporal sequence between the administration of the drug and the occurrence of the AE. This event does not match the ARs described for the drug and may be explained by alternative causes.
- **Unrelated:** There is no reasonable temporal sequence between the administration of the drug and the occurrence of the AE. This event does not match the ARs described for the drug and may be explained by alternative causes.

For expeditious reporting, the categories "definitive," "probable," and "possible" from the Karch and Lasagna (1977) algorithm will be considered related, and the category "conditional or unlikely" will be considered unrelated.

Determining the potential relationship to the study treatment is the responsibility of the principal investigator at the research site or the person designated by them.

Serious Adverse Event (SAE)

Any harmful incident affecting the health of a subject that, at any dose:

- Requires hospitalization or prolongation of hospitalization,
- Causes permanent or significant disability or incapacity,
- Leads to a congenital anomaly or malformation,
- Poses a threat to life or results in death,
- Is considered medically significant.

For reporting purposes, any suspected AE or AR deemed medically important will also be treated as serious, even if they do not meet the previous criteria, including medical events requiring intervention to prevent any of the aforementioned outcomes. Any suspected transmission of an infectious agent via a medication will also be considered serious.

The term "life-threatening" refers to the investigator's opinion that the patient is at real risk of death at the time of the AE or AR; it does not refer to the hypothetical possibility that the AE/AR could have led to death if it had been more severe.

It should not be confused with the term "severe," which refers to the intensity of the AE or AR (mild/moderate/severe).

Serious and Unexpected Adverse Reaction (SUSAR)

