A serious adverse reaction whose nature, severity, or outcome is inconsistent with the reference safety information. In this case, the product information (SmPC) will be used as the reference.

SAEs that meet the SUSAR criteria and are associated with blinded studies should be reported to Health Authorities with the open-label unblinding.

Adverse Events of Special Interest in this Study

Infections, events that lead to the discontinuation of the study treatment, and the development of diabetes mellitus or hypertension are considered of special interest.

Expected Adverse Reactions Not Clinically Significant in this Study

The following adverse reactions are commonly associated with the study medication in clinical practice. They will be recorded in the patient's medical history, but for reporting purposes, they will not be collected in the e-CRF unless, in the investigator's clinical judgment, they meet the severity criteria.

These include the occurrence of hirsutism, moon face, acne, insomnia, weight gain, buffalo hump, and stretch marks.

II) Methods and Schedule for Evaluation, Recording, and Analysis of Safety Parameters

Adverse events will be recorded from the administration of the study drug until the end of the patient's participation in the study, whether spontaneously reported by the patient or detected during study visits.

Follow-up of all ARs, SAEs, and SAREs will be conducted until resolution, irreversibility, or study completion, whichever occurs first.

All ARs, SAEs, SAREs must be documented in the patient's medical history and in the e-CRF, except for clinically insignificant ARs described above.

Any pregnancy occurring during the study and its outcome must be recorded and followed to rule out congenital anomalies or malformations. Information will be gathered on:

- Normal birth, spontaneous or therapeutic abortion (any congenital anomaly detected in the aborted fetus should be documented), stillbirth, congenital anomaly.
- Neonatal deaths within 30 days of birth.
- Infant death after 30 days if the investigator suspects it is related to in-utero exposure to the study medication.
- All infants born after fetal exposure must be followed during the first 12 months after delivery.

Any exacerbation of a pre-existing disease occurring after the start of the study treatment is also considered an adverse event.

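### Every causality category counted as related requires a match with already described reactions; this conflicts with the SUSAR definition and puts expedited reporting of serious events of undescribed nature at risk

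*Combined protocol and SAP*

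**What the plan says.** Section 11.I (Causality Criteria) sets out five categories.

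- *Definitive* requires, among other things, "This event matches the ARs described" for the drug, together with improvement on stopping, recurrence on re-administration and no alternative cause.
- *Probable*: "This event matches the ARs described for the drug, improves after treatment is interrupted, and cannot be explained by other alternatives".
- *Possible*: "This event matches the ARs described for the drug but may be explained by alternative causes".
- *Conditional or unlikely*: "This event does not match the ARs described for the drug and may be explained by alternative causes".
- *Unrelated* is the same as the last, but without a reasonable time sequence.

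For expedited reporting, the first three count as related, and "the category 'conditional or unlikely' will be considered unrelated".

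Later in section 11.I a SUSAR is defined as "A serious adverse reaction whose nature, severity, or outcome is inconsistent with the reference safety information", with the SmPC as the reference.

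On who decides, section 11.I first states that "The sponsor will classify adverse events based on their causal relationship with the drug", and after the category list that "Determining the potential relationship to the study treatment is the responsibility of the principal investigator" or a designee.

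**The concern.** Relatedness and expectedness are separate questions. The first asks whether the drug may have caused the event, the second whether the event is already known. The scale builds part of the second question into the first. A serious event of a kind not yet described for the drug fails the relatedness test because it is new, and so may never reach the step at which its novelty would make it a SUSAR.

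The stake is the timing of reports to the regulator and the ethics committee. Section 11.III sets 15 calendar days for a suspected SARE, or 7 if it is fatal or life-threatening, and both limits presuppose that someone has called the event related. The experimental element is three 0.5 g intravenous boluses, and section 5.II describes the earlier bolus studies in ulcerative colitis as having limited patient numbers and varying regimens. A harm not seen in those studies is what expedited reporting should pick up.

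**Working it through.** The plan gives no figure to reproduce. The check runs the category definitions over every pattern they distinguish and sets the result beside the SUSAR definition.

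**Inputs**, all from section 11.I: a reasonable time sequence (held as present), match with described reactions (yes/no), possible alternative cause (yes/no), improvement on withdrawal (yes/no). Recurrence on re-administration only separates *definitive* from *probable*, and both count as related, so it is left out. This gives 2 × 2 × 2 = 8 patterns.

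| Match | Alternative cause | Improves on withdrawal | Category | Expedited status |
|---|---|---|---|---|
| yes | yes | yes | possible | related |
| yes | yes | no | possible | related |
| yes | no | yes | probable or definitive | related |
| yes | no | no | none | undefined |
| no | yes | yes | conditional or unlikely | unrelated |
| no | yes | no | conditional or unlikely | unrelated |
| no | no | yes | none | undefined |
| no | no | no | none | undefined |

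**Counts.** Of the 8 patterns, 3 are related, 2 unrelated and 3 have no category. Of the 4 non-matching patterns, 0 are related, 2 are unrelated and 2 have no category.

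**Three consequences.**

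1. A non-matching event that might have another cause is treated as unrelated.
2. A non-matching event with plausible timing and no other explanation, arguably the strongest signal of a new harm, has no category.
3. A matching event with no other explanation that does not improve after the drug is stopped, such as a fatal one, also has no category. *Probable* and *definitive* require improvement, and *possible* requires an alternative cause. The scale thus grades that event less clearly than one that does have a competing explanation.

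**Against the SUSAR definition.** A SUSAR must be a reaction and must be inconsistent with the SmPC in nature, severity or outcome. An event of a described type but unexpected severity or outcome can match, be related and qualify. For unexpected nature, the scale demands consistency with known reactions while the SUSAR definition looks for inconsistency.

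**Who decides.** One sentence has the sponsor classify by the scale. Another makes the relationship the investigator's responsibility and gives no criteria of its own. Section 11.II then ties SAE reporting partly to the investigator considering the event related. If an investigator suspects the drug and the sponsor's grading gives *conditional or unlikely*, nothing says which stands.

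**The case against.** The strongest reply is that the plan leaves other routes open, and much of it stands.

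- **The investigator's route.** Section 11.II equates a SARE with an SAE that the investigator considers related. The Pharmacovigilance Unit must report all SAREs, and the section 11.III deadlines attach to a suspected SARE, not to a scale category. An investigator who suspects the drug can therefore start the process. This is a real safeguard, but it is incomplete: the only stated criteria are those of the scale, and the related/unrelated split for expedited reporting is written in the scale's terms.
- **Visibility.** SAEs go into the e-CRF (section 11.II), and the annual safety reports cover SAEs as well as SAREs (section 11.III). Such events are not hidden, but an annual listing does not replace a 7- or 15-day report.
- **Source of described reactions.** The causality text does not say where the reactions must be described; the SmPC is named only for expectedness. A reaction described elsewhere but absent from the SmPC could match and still be unexpected. This narrows the gap without closing it.
- **General commitment to GCP and regulations.** It opens section 11, but it does not tell staff to override a specific operating rule.

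A reader might infer that a reaction of unexpected nature can never be reported as a SUSAR, or that every such event would be filed as unrelated. The documents do not support either. The investigator's route exists, and an event with no alternative cause is left without a category, not filed as unrelated. A reader might also infer that such an event arising more than 30 days after the last dose would go unreported. That sentence in section 11.II is too unclear to bear the weight, and it keeps an exception for medically important events.

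**Conclusion.** The concern holds as a contradiction within section 11. The scale used for expedited reporting admits no non-matching pattern to a related category (0 of 4), while the SUSAR definition depends on some such events being related. The scale also leaves 3 of its 8 patterns with no category, one of which is a matching event.

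The consequence is a risk of missed or late expedited reports, not a bar on reporting. It is confined to events of undescribed nature and to the uncategorised matching event; known reactions of unexpected severity or outcome can still become SUSARs if they fall in a related category. The result assumes that the scale is applied as written and that the described reactions are broadly those in the SmPC. The documents give no basis for estimating how many events would be affected. The primary endpoint and its analysis are not touched.

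**What to change.** Amend section 11.I as follows.

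- **(a) Separate the two questions.** For expedited reporting, define related as a reasonable possibility that the study treatment caused the event, whether or not the reaction is already described. Assess expectedness afterwards, against the SmPC. Reword the sentence that makes *conditional or unlikely* automatically unrelated to agree with this.
- **(b) Close the gaps.** Place any event with a reasonable time sequence and no alternative cause in *possible* or higher, whether or not it matches described reactions or improves on withdrawal.
- **(c) Settle who decides.** State that a related judgement by either the investigator or the sponsor makes the event related, and that the sponsor may not downgrade the investigator's judgement.

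A time sequence alone should not be sufficient where another cause, such as the underlying colitis, is the more likely explanation. Section 11.II counts any exacerbation of a pre-existing disease after treatment starts as an adverse event, and hospitalization makes an event serious. Under a timing-only rule, admissions for colitis flares could be classed as related in bulk.

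The cost is a few sentences in one section and some additional expedited reports, whose number cannot be estimated from the documents.

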7. STUDY DESIGN

I) Primary and Secondary Variables

Primary Outcome Variable:

Clinical and endoscopic remission, steroid-free at 8 and 54 weeks, without rescue treatment and without the need for steroids up to week 54.

Secondary Variables (Variables of Interest):

- **Clinical Remission** (assessed at weeks 8 and 54): Mayo Score \leq 2 points with no individual variable $>$ 1.
- **Endoscopic Remission**: Mayo endoscopic subscore of 0 or 1.
- **Clinical Response** (assessed at weeks 8 and 54): a reduction in the Mayo score by at least 3 points and at least 30%, with a decrease in the rectal bleeding subscore of at least 1 point or to an absolute value of 0 or 1.
- **Early Clinical Response**: a decrease in the clinical Mayo subscore by at least 3 points and at least 30%, with a decrease in the rectal bleeding subscore of at least 1 point or to an absolute value of 0 or 1, at days 3 and 7 of corticosteroid treatment.
- **Relapse**: reappearance of symptoms, defined as a Mayo clinical subscore $>$ 2. The time of relapse from treatment initiation will be recorded.
- **Corticosteroid Dependency**: relapse during prednisone tapering or within three months after corticosteroid discontinuation.
- **Rescue Treatment**: restart or increase of the established corticosteroid dose (including topically acting oral corticosteroids) or initiation of any treatment for ulcerative colitis other than mesalazine, including biological agents (infliximab, adalimumab, golimumab, vedolizumab), calcineurin inhibitors (cyclosporine, tacrolimus), thiopurines (azathioprine, mercaptopurine), methotrexate, leukapheresis, or colectomy.
- **Need for Surgery** and time to surgery from treatment initiation.
- **Adverse Event Rate** and rate of severe adverse events (including hospitalizations) recorded throughout the study duration.
- **Fecal Calprotectin Determination**.

II) Study Design

This is a Phase IV, controlled, prospective, randomized, open, multicenter study to compare two corticosteroid treatment regimens for moderate UC flares.

III) Estimated Number of Subjects, Sample Size, and Justification

Study Subjects: Adult patients of both sexes with active moderate ulcerative colitis, with or without maintenance treatment or with oral/topical mesalazine.

Sample Size: 148 patients.

Sample Size Calculation:

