8. SUBJECT SELECTION AND WITHDRAWAL

I) Inclusion Criteria

1. Diagnosis of Ulcerative Colitis based on the European Crohn's and Colitis Organization criteria.
2. Patients aged 18 years or older.
3. Disease extension of at least left-sided (involvement >25 cm from the anal margin).
4. Moderate flare according to the Mayo Index (score ≥ 6 and ≤ 10).
5. No maintenance treatment or only 5-ASA oral and/or topical treatment.
6. Patient has the capacity to understand study requirements and provide informed consent.
7. Signed Informed Consent.

II) Exclusion Criteria

1. Previous or current treatment with thiopurines, calcineurin inhibitors, methotrexate, and/or biological agents.
2. Systemic corticosteroid use in the last 6 months (excluding topical oral corticosteroids).
3. Severe active or uncontrolled systemic infection, serious diseases, or medical conditions that may interfere with the patient's eligibility or treatment.
4. Uncontrolled diabetes mellitus or hypertension.
5. Psychiatric disorder or any other uncontrolled condition that contraindicates steroid treatment.
6. Pregnancy, lactation, or intention to become pregnant during the study period.
7. History of allergic reactions attributed to corticosteroids.

III) Withdrawal Criteria and Analysis

Premature termination of the trial will occur whenever the clinical trial is terminated before meeting the conditions outlined in the protocol.

Patients may be withdrawn from the study before reaching week 54 (end of follow-up) for any of the following reasons:

- **Patient Decision:** Patients are free to withdraw from the study at any time without any penalty or impact on their disease management or subsequent treatments.
- **Pregnancy.**
- **Serious Complications Due to Steroid Treatment.**
- **Lack of Early Clinical Response.**
- **Failure to Achieve Clinical and Endoscopic Remission, Steroid-Free at Week 8.**
- **Clinical Worsening and Need for Rescue Treatment at the Investigator's Discretion.**
- **Major Protocol Deviation.**

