Any abnormal result in laboratory tests that the investigator considers clinically significant and requires dose adjustment, temporary or permanent interruption of the study treatment, or any type of intervention or diagnostic evaluation to assess the risk to the patient, will be recorded as an adverse event and must be properly investigated and monitored.

In the case of an SAE that must be reported to the Pharmacovigilance Unit, or a pregnancy case, a member of the investigator team will complete and sign the SAE or pregnancy notification form (see Annexes 5 and 6) and send it via fax immediately, and

within 24 hours of knowledge of the event, to:

[name] / [name]
UICEC, Hospital Universitario de Canarias
[contact]
[contact]

The Pharmacovigilance Unit will review the received form and, if necessary, will request additional information from the investigator.

Once additional information is obtained on the SAE/pregnancy, or the event is resolved or unlikely to change, a follow-up report should be completed and sent, via fax, to the Pharmacovigilance Unit.

Any SAE should be reported within 30 days of the last dose of medication (without time limit) if the investigator considers the SAE related to the study treatment (i.e., if it is an SARE) or if it is medically important.

The Pharmacovigilance Unit is responsible for reporting to the AEMPS (Clinical Trials Area of the Subdirectorate General of Human Medicines) and the Ethics Committee all SAREs that occur in the study, following the procedure established by current legislation.

III) Procedures for Obtaining Reports on Adverse Events and Intercurrent Diseases and for Recording and Communicating Them

The maximum reporting period for a suspected SARE case will be 15 calendar days from the moment the sponsor becomes aware of it.

If the suspected SARE has caused the death of the patient or put their life in danger, the sponsor will send the information within 7 calendar days from when they become aware of it and will complete the information, if possible, within the next 8 days.

Annual safety reports, including SAREs and SAEs recorded in the study, will be sent to the AEMPS (Clinical Trials Area of the Subdirectorate General of Human Medicines) and the Ethics Committee within the timeframes established by current legislation.

The project manager will communicate any safety information that could affect the safety of study subjects to the investigators as soon as possible.

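### The plan does not say whether adverse events are collected after withdrawal for treatment failure, so adverse-event rates may rest on unequal observation time in the two arms

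*Combined protocol and SAP*

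**What the plan says.** Three places describe when safety data are collected.

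- Section 11.II, recording of all adverse events: "Adverse events will be recorded from the administration of the study drug until the end of the patient's participation in the study".
- Section 7.I, definition of the adverse-event variables: "rate of severe adverse events (including hospitalizations) recorded throughout the study duration".
- Section 11.II, reporting of serious events: "Any SAE should be reported within 30 days of the last dose of medication (without time limit". The bracketed words appear to extend the period for serious events judged related or medically important, but the sentence is unclear.

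On leaving the study, section 8.III says: "Patients may be withdrawn from the study before reaching week 54 (end of follow-up) for any of the following reasons". The reasons include "Lack of Early Clinical Response", which section 7.I assesses "at days 3 and 7 of corticosteroid treatment"; "Failure to Achieve Clinical and Endoscopic Remission, Steroid-Free at Week 8"; and clinical worsening with need for rescue. Section 7.VII lists the same three reasons.

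Section 12 assigns chi-squared and t-tests to most secondary objectives. It keeps Kaplan-Meier curves and the log-rank test for relapse, steroid dependency and surgery. It does not say how adverse events will be compared, although their rates are secondary objectives (section 6).

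Two further passages concern patients affected by an adverse event. Section 5.III follows those taken off medication to the end of the study; section 11.IV excludes comparable patients from the study.

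**The concern.** Section 8.III describes leaving the study before the end of follow-up, not merely stopping the assigned treatment. Read with the recording rule in section 11.II, a patient withdrawn for failure at day 7 or week 8 may contribute no new adverse events afterwards. Such a patient has recently had high steroid exposure and may be starting rescue treatment. Section 11.I names infection, new diabetes and new hypertension as events of special interest, and these may appear after that point.

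Two things are at stake. First, harms may be under-recorded in either arm, whatever the difference between arms. Second, those who stay to week 54 are mainly the successes, and the plan expects twice the proportion of successes in the bolus arm. Event rates that ignore time observed could then differ between arms with no difference in true risk. The comparison matters because section 5.II presents the bolus as a strategy that does not increase the risk of adverse events.

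**Working it through.** The plan states no adverse-event rate, person-time or safety sample size, so there is no figure of its own to reproduce. What follows is an illustration.

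**Inputs from the documents.** Success is 20% in the oral arm (section 7.III) and 40% in the bolus arm (section 12, interim analysis). N is 148, allocated 1:1, so 74 per arm. Follow-up ends at week 54. Possible exits for failure are days 3–7 and week 8.

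**Assumptions.** The share *w* of failures that leave, the time at which they leave, and the event hazard *h* are not in the documents.

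**How many patients could be affected.** Expected failures on the primary endpoint are 74 × 0.8 + 74 × 0.6 = 59.2 + 44.4 = 103.6, about 104 of 148 (70%). This includes patients who remit at week 8 and relapse later, so fewer than this fail at week 8.

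**Mean observation.** With success *p* and exit at week 8: 54*p* + (1 − *p*)[8*w* + 54(1 − *w*)].

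| Share of failures leaving at week 8 | Oral, weeks | Bolus, weeks | Ratio |
|---|---|---|---|
| 0% | 54.0 | 54.0 | 1.00 |
| 25% | 44.8 | 47.1 | 1.05 |
| 50% | 35.6 | 40.2 | 1.13 |
| 75% | 26.4 | 33.3 | 1.26 |
| 100% | 17.2 | 26.4 | 1.53 |

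For the last row: 0.2 × 54 + 0.8 × 8 = 17.2 and 0.4 × 54 + 0.6 × 8 = 26.4. If every failure left at day 7, the figures would be 0.2 × 54 + 0.8 × 1 = 11.6 and 0.4 × 54 + 0.6 × 1 = 22.2, ratio 1.91.

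**Effect on the proportion with a recorded event.** Assume the same constant hazard in both arms and all failures leaving at week 8: P = (1 − *p*)(1 − e^(−8*h*)) + *p*(1 − e^(−54*h*)).

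- At *h* = 1% per week, oral: 0.8 × 0.0769 + 0.2 × 0.4173 = 14.5%.
- At *h* = 1% per week, bolus: 0.6 × 0.0769 + 0.4 × 0.4173 = 21.3%.
- The gap is 6.8 points. It is 3.9 points at 0.5% per week and 10.3 at 2%.
- If half of the failures leave, the gap at 1% is 3.4 points.

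The 6.8 points equal 0.2 × (e^(−0.08) − e^(−0.54)) = 0.2 × (0.923 − 0.583), so all of it accrues between weeks 8 and 54. If events occur only in the first 8 weeks, week-8 exits produce no gap; only earlier exits could.

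**The serious-event window.** The taper steps 60-50-40-30-20-15-10-5 take 8 weeks, to about day 56, so 30 days more is about day 86. That lies inside participation for a patient who stays to week 54 (day 378), but after it for a patient withdrawn at week 8, or at day 7 if dosing continues. If medication meant only the bolus (last dose day 3), the window would end about day 33: inside participation for a week-8 exit, outside it for a day-7 exit.

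**Start of recording.** Recording starts with the study drug, and section 7.V describes the study medication as the intravenous bolus. The starting point in the oral arm is therefore not defined.

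**The case against.** The case against is substantial, and it rules out several stronger readings that a reader might infer.

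- *That the arms will be observed for unequal times.* Section 8.III is permissive. The imbalance needs sites to use the option and failure to differ by arm. With no withdrawals, observation is 54 weeks in both arms.
- *That 17.2 v 26.4 weeks is a planning estimate.* The 20% and 40% describe remission at week 8 sustained to week 54. Patients who remit and relapse later cannot have left at week 8 for failing to remit, and section 5.I expects relapse to be common. No week-8 remission rate is given. The figures are the extreme case for the week-8 route.
- *That the comparison is biased against the bolus.* Section 11.II counts exacerbation of a pre-existing disease as an adverse event, and section 7.I includes hospitalisations. Failure may itself generate events, more of them in the arm with more failures. A constant hazard to week 54, well after the planned 8 weeks of treatment (section 7.VI), also has no source in the documents.
- *That the 30-day rule contradicts the recording rule.* One governs reporting of serious events, the other recording of all events. Both can hold. They are unreconciled only for patients whose participation ends before the window closes.
- *That harms in failures would all go unrecorded.* The unlimited clause may cover related or medically important serious events, and section 11.II follows reactions and serious events already present to resolution, irreversibility or study completion.
- *That section 12 fixes a crude comparison of proportions.* It speaks of most secondary objectives and never names adverse events. The method is unspecified.

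What remains is the omission. Following existing events does not capture new ones, and section 5.III concerns stops caused by an adverse event, not by failure. The primary endpoint is little affected, since section 12 uses non-response imputation.

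**Conclusion.** The concern holds as a gap in the plan and a risk to the harm comparison, not as a demonstrated bias. The body of the protocol does not say whether adverse events are collected after withdrawal for treatment failure. The safety windows in sections 7.I and 11.II are not aligned for those patients, and no time-based analysis of adverse events is named. The annexes, including the procedures summary in Annex 8, were not in the text reviewed.

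The possible imbalance in mean observation at week-8 exit runs from none (ratio 1.00) through 1.13 to 1.53 as the share of failures leaving goes from none to half to all, taking the planned success rates as true. Any effect on event proportions rests further on an assumed hazard, can be nil, and could go in either direction. The point should be fixed because adverse-event rates are secondary objectives and the remedy is cheap. It does not change the sample size.

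**What to change.** 1. **Section 12.** Prespecify the main between-arm adverse-event comparison as first dose to week 8, with time to first event or events per patient-week to week 54 as support. This needs no new data. It does not recover events after an exit at days 3–7, and censoring at failure may be informative, so it does not replace step 2.
2. **Section 11.II.** Separate stopping the assigned treatment from leaving follow-up. Start recording at the first dose of the assigned steroid regimen in both arms. Collect adverse events in withdrawn patients to at least 30 days after the last steroid dose, and serious and special-interest events to week 54, unless consent is withdrawn. The cost is a phone call or record check per withdrawn patient. If everyone is followed to week 54, mean observation is 54 weeks in both arms.
3. **One safety window.** Reconcile section 7.I with the two statements in section 11.II, and clarify the clause on unlimited reporting. Reconcile section 5.III with section 11.IV on what follows an adverse event that affects study medication. This costs protocol wording only.
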